
FOOTNOTES:
 
a: The screening visit should occur within approximately 4 weeks before the Week 0 visit.
 
b: All Week 48 study procedures should be performed on any subject who terminates the study prior to Week 48, except for collection of serum for biomarkers. If a subject terminates post-Week 48, sites should make every effort to conduct the Week 56 assessments.
 
c: All study procedures and evaluations should be completed before administration of study drug. Assessments for subjects who discontinue study agent administration or withdraw from the study are discussed in Section 10.2.
 
d: Women of childbearing potential must have a negative urine pregnancy test before randomization, before study drug administration, and at all study visits.
 
e: The eC-SSRS should be completed by the subject before any tests, procedures, or other consultations to prevent influencing subject perceptions,
 
f: A tuberculin skin test is additionally required if the QuantiFERON-TB Gold test is not approved/registered in the country in which this study is being conducted.
 
g: Laboratory tests are listed in Section 9.6.
 
h: Subjects must fast (ie, no food or beverages [except water]) for at least 8 hours before blood is drawn for lipid panel. All other visits can be nonfasting.
 
i: All blood samples must be collected before study agent administration at visits when a study agent administration is scheduled. Details will be provided in the Laboratory Manual.
 
j Serum biomarker measurements will include but are not limited to: serum IL-17A, IL-17F, and IL-22. For subjects who discontinue from the study prior to Week 48, serum is not to be collected for measurement of biomarkers.
 
k Biopsy samples for RNA and tissue histology will be collected only from subjects who consent to participate in the optional biopsy substudy. Biopsy samples will be used to assess the cellular and molecular profiles of psoriatic skin lesions at baseline and during treatment.
 
[REDACTED]
 
m: Blood samples for genetic (DNA) analyses will be collected only from subjects who sign a separate consent form to participate in the genetic (DNA) evaluations.
																		

ABBREVIATIONS

BCG	Bacille Calmette-Guérin
BSA	body surface area
CSR	clinical study report
DBL	database lock
ECG	electrocardiogram
eCRF	electronic case report form
eC-SSRS	electronic Columbia-Suicide Severity Rating Scale
eDC	electronic data capture

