11.8. Safety Analyses

Safety data, including but not limited to, AEs, SAEs, infections, serious infections, changes in laboratory assessments, changes in vital signs, changes in electrocardiograms (ECGs), and suicidal ideation and behavior based on eC-SSRS will be summarized. Treatment-emergent AEs will be summarized by treatment group and Medical Dictionary for Regulatory Activities (MedDRA) system organ class and preferred terms.

Safety Definitions

Injection Site Reactions

An injection site reaction is any unfavorable or unintended sign that occurs at an injection site and will be recorded as an AE. Detailed instructions for the evaluation of injection site reactions are in the Trial Center File.

Adverse Events

The verbatim terms used in the eCRF by investigators to identify AEs will be coded using MedDRA. All reported AEs with onset during the treatment phase (ie, treatment-emergent AEs, and AEs that have worsened since baseline) will be included in the analysis.

Summaries, listings, or subject narratives may be provided, as appropriate, for those subjects who die, who discontinue treatment due to an AE, or who experience a severe AE or an SAE.

The following analyses will be used to assess the safety of subjects in the study:

- The incidence and type of AEs.
- The incidence and type of SAEs.
- The incidence and type of infections.
- The incidence and type of reasonably related AEs.
- The incidence and type of injection site reactions.
- The laboratory parameters and change from baseline in laboratory parameters (hematology and chemistry).

In addition, National Cancer Institute-Common Terminology Criteria for Adverse Events (NCI-CTCAE) grades will be used in the summary of laboratory data. A listing of subjects with post-baseline abnormal laboratory results based on NCI-CTCAE grades will also be provided.

Vital Signs

Descriptive statistics of heart rate and blood pressure (systolic and diastolic) values and changes from baseline will be summarized by treatment group.

Electrocardiogram

Electrocardiogram data will be collected at baseline and Weeks 16 and 48. Electrocardiogram data at each visit and change from baseline will be summarized by ECG parameters and by treatment group.

Electronic Columbia-Suicide Severity Rating Scale

Suicide-related thoughts and behaviors based on the eC-SSRS will be summarized descriptively by treatment group.

Anticipated Events

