12.1. Definitions

12.1.1. Adverse Event Definitions and Classifications

Adverse Event

An AE is any untoward medical occurrence in a clinical study subject administered a medicinal (investigational or non-investigational) product. An AE does not necessarily have a causal relationship with the treatment. An AE can therefore be any unfavorable and unintended sign (including an abnormal finding), symptom, or disease temporally associated with the use of a medicinal (investigational or non-investigational) product, whether or not related to that medicinal (investigational or non-investigational) product. (Definition per International Conference on Harmonisation [ICH])

This includes any occurrence that is new in onset or aggravated in severity or frequency from the baseline condition, or abnormal results of diagnostic procedures, including laboratory test abnormalities.

Note: The sponsor collects AEs starting with the signing of the ICF (refer to Section [12.3.1](#), All Adverse Events, for time of last AE recording).

Serious Adverse Event

An SAE, based on ICH and European Union Guidelines on Pharmacovigilance for Medicinal Products for Human Use, is any untoward medical occurrence that at any dose:

- Results in death
- Is life-threatening
(The subject was at risk of death at the time of the event. It does not refer to an event that hypothetically might have caused death if it were more severe.)
- Requires inpatient hospitalization or prolongation of existing hospitalization
- Results in persistent or significant disability/incapacity
- Is a congenital anomaly/birth defect
- Is a suspected transmission of any infectious agent via a medicinal product
- Is Medically Important*

*Medical and scientific judgment should be exercised in deciding whether expedited reporting is also appropriate in other situations, such as important medical events that may not be immediately life threatening or result in death or hospitalization but may jeopardize the subject or may require intervention to prevent one of the other outcomes listed in the definition above. These should usually be considered serious.

If a serious and unexpected AE occurs for which there is evidence suggesting a causal relationship between the study drug and the event (eg, death from anaphylaxis), the event must be reported as a serious and unexpected suspected adverse reaction.

Unlisted (Unexpected) Adverse Event/Reference Safety Information

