6.1. Adverse Events

The verbatim terms used in the CRF by investigators to identify adverse events will be coded using the Medical Dictionary for Regulatory Activities (MedDRA). Any AE starting at or after the initial administration of study agent through the end of the trial is considered to be treatment emergent. If the event occurs on the day of the initial administration of study agent, and either event time or time of administration are missing, then the event will be assumed to be treatment emergent. If the event date is recorded as partial or completely missing, then the event will be considered to be treatment emergent unless it is known to be prior to the first administration of study agent based on partial onset date or resolution date. All reported treatment-emergent adverse events will be included in the analysis. For each adverse event, the number and percentage of subjects who experience at least 1 occurrence of the given event will be summarized by treatment group. In addition, event rate per 100 subject-years of follow-up for serious infections will be provided.

Summary tables will be provided for:

- AEs
- Serious AEs (SAEs)
- AEs leading to discontinuation of study agent administration
- AEs by severity
- AEs by relationship to study agent
- Infections
- Serious infections
- Infections treated with oral or parenteral antimicrobial treatment parenteral antibiotics
- Injection-site reactions
- AEs of psoriasis

In addition to the summary tables, listings will be provided for subjects who:

- Had SAEs
- Had AEs leading to discontinuation of study agent administration
- Had AEs of severe intensity
- Had serum sickness-like reactions or anaphylactic reactions

Any unfavorable or unintended sign that occurs at the injection site is an injection site reaction and will be recorded as an injection site reaction by the investigator on the eCRF. An infection is defined as any AE that was recorded as an infection by the investigator on the eCRF.

The treatment-emergent adverse events of psoriasis include any event of erythrodermic psoriasis, pustular psoriasis, guttate psoriasis, and worsening or exacerbation of psoriasis. Incidence of these events will be summarized.

Since safety should be assessed relative to exposure and follow-up, most AE summary tables will include average weeks of follow-up and average number of study agent administrations for each treatment group.

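### SAP 6.1 omits the protocol's limb for events that worsen from baseline, so an adverse event that begins in screening and worsens after dosing can be missing from the AE summary tables

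*SAP*

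**What the plan says.** SAP 6.1 defines treatment emergence by when the event starts: "Any AE starting at or after the initial administration of study agent through the end of the trial is considered to be treatment emergent". For partial or missing dates there is a default: "the event will be considered to be treatment emergent unless it is known to be prior to the first administration of study agent". The section then states "All reported treatment-emergent adverse events will be included in the analysis" and lists ten summary tables, among them AEs, SAEs, AEs leading to discontinuation, AEs by severity, AEs by relationship, and three on infections. It has no general clause for events that worsen.

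Protocol 11.8 describes the AE analysis differently. It takes in "All reported AEs with onset during the treatment phase (ie, treatment-emergent AEs, and AEs that have worsened since baseline", where the last words inside the bracket name a second kind of event beside the treatment-emergent ones.

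Two further provisions bear on which events exist in the database. Protocol 12.1.1 says "The sponsor collects AEs starting with the signing of the ICF", and footnote a of the Time and Events Schedule says "The screening visit should occur within approximately 4 weeks before the Week 0 visit". Protocol 12.1.1 also says of the AE definition: "This includes any occurrence that is new in onset or aggravated in severity or frequency from the baseline condition".

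**The concern.** Because collection starts at consent, the database will hold AEs whose onset lies in screening. Some may become worse after the first injection. That worsening is information about tolerability on drug, and the protocol says it belongs in the analysis. Under the SAP as written, whether it appears in a table depends on how the site entered it, not on what happened to the subject.

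Safety and tolerability of guselkumab is a stated secondary objective, and the AE summaries are the main output for it. For some categories they are the only planned summary. SAP 6.1 defines an infection as an AE the investigator recorded as one, and SAP 6.3 analyses physical examination findings only through the AEs they generate. No separate table would pick up a worsening of that kind.

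**Working it through.** No figure in the plan is at issue, so the check sets the rules side by side and then asks which outputs depend on them.

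**Step 1. Follow one event through both rules.** Take an AE that begins after consent and before the first injection, and becomes worse after it.

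| How it is recorded | Protocol 11.8 | SAP 6.1 summary tables |
|---|---|---|
| One record, complete onset date in screening | In, as an event worse than at baseline | Out: it starts before first administration |
| One record, onset partial or missing and not known to precede dosing | In | In, by the date default |
| Worsening entered as a new AE with a post-dose onset date | In | In |

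The two documents part company only in the first row.

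**Step 2. Is the first row excluded by instruction?** Three provisions lean toward a new record. Protocol 12.1.1 counts an aggravation from the baseline condition as an AE. Protocol 9.6 wants clinically relevant changes during the study on the AE section of the eCRF. Protocol 9.6.1 wants new or worsening, clinically significant eC-SSRS findings reported there. None of them says that a worsened AE already in the database is closed and reopened with a new onset date. The one express new-record instruction is narrow: in Protocol 12.3.2, an AE that prolongs a hospitalization planned beforehand is to be reported as a new SAE. The first row is therefore permitted.

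**Step 3. Which outputs depend on the definition?**
- Dependent: the AE summary tables of SAP 6.1 and the serious-infection rate per 100 subject-years. The table of AEs of psoriasis is a partial exception, since SAP 6.1 names worsening or exacerbation as a treatment-emergent event there.
- Not expressly limited to treatment-emergent events: the SAP 6.1 listings of subjects with SAEs, AEs leading to discontinuation and severe AEs.
- Built on other data: worst toxicity grade and change from baseline in laboratory values (SAP 6.2), vital signs (6.3), ECG (6.4), and the eC-SSRS shift from a score-based baseline to the worst post-baseline category (6.5), which uses questionnaire results as well as AEs.

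**Step 4. Size.** Neither document gives the number of screening-onset AEs, the share that worsen on drug, or the share kept as a single record. The number lost runs from zero (every worsening entered as a new AE) to all such events with a known pre-dose onset (every one kept as a single record). Nothing in the documents narrows that range.

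**The case against.** The best answer is that nothing is lost, because a worsening is itself an AE under Protocol 12.1.1 and would carry its own post-dose onset. SAP 6.1 treats worsening of psoriasis in this way although every subject had psoriasis before dosing. Protocol 11.8 places worsened events under the phrase about onset during treatment, so the worsening may be meant as the onset, which would fit the SAP's start-date rule. Protocol 11 also leaves specific details to the SAP. This is a fair reading, and it may describe what sites did. But it rests on a recording convention that neither document states, and practice could differ between sites. The protocol's ambiguity is a reason to write the rule down.

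It can also be said that the rule is the same in both arms and that no formal safety test is planned. Both are true. An equal rule can still hide a difference if one drug aggravates existing conditions more than the other.

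Three stronger readings are tempting and should be resisted:
- A reader might infer that such events vanish from all safety reporting. They do not: Step 3 lists outputs that do not use the definition, and Protocol 11.8 allows narratives for subjects with severe AEs, SAEs or discontinuation due to an AE.
- A reader might see a second loss in the window, which is the treatment phase in the protocol and the end of the trial in the SAP. The SAP window is the wider one and loses no events.
- A reader might attach a number of subjects or SAEs to the gap. Any such number would rest on assumed rates with no source in the documents.

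**Conclusion.** The mismatch is real and limited. SAP 6.1 leaves out a category that Protocol 11.8 includes in the AE analysis, and gives no reason. The consequence is a possible undercount in the SAP 6.1 AE summary tables. It is confined to events that start in the roughly 4-week screening period, have an onset known to precede dosing, worsen after it, and stay as one record. The size cannot be estimated and may be zero.

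The conclusion rests on two assumptions: that Protocol 11.8 means worsened events to be counted whatever their original onset date, and that no instruction outside these documents requires a new record for a worsening. If such an instruction exists and was followed, the difference is one of wording only. It is worth correcting either way, because the correction is small and a secondary objective is reported through these tables.

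**What to change.** In SAP 6.1, add a second limb to the treatment-emergent definition: or onset before the first administration with worsening from baseline after it. Keep the SAP window through the end of the trial (Week 56), and change the treatment-phase wording in Protocol 11.8 to match. The protocol's limb speaks of worsening and does not separately mention becoming serious, so alignment needs no more than this.

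Stating that each worsening is entered as a new AE would also close the gap, but it would come late: the SAP's amendment history says that enrollment is complete, so records already exist. The derivation rule covers both recording practices. Before database lock, confirm that the eCRF shows when an event worsened; the documents do not say whether it does. Where it does not, the affected screening-onset records would need a query.

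The cost is one extra derivation rule and slightly higher AE counts. No assessment, sample size or efficacy analysis changes.

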6.2. Clinical Laboratory Tests

All clinical laboratory reports will be displayed for the subjects included in the safety analysis set. The clinical laboratory parameters to be evaluated by the central laboratory include but are not limited to:

- **Hematology:** hemoglobin, hematocrit, lymphocytes, neutrophils, platelets, red blood cell (RBC) count and white blood cell (WBC) count.
- **Chemistry:** albumin, alkaline phosphatase, alanine aminotransferase, aspartate aminotransferase, total carbon dioxide (CO₂), total bilirubin, blood urea nitrogen/urea, calcium, chloride, creatinine, glucose, potassium, total protein, sodium.

Box plots of laboratory measurements and change from baseline will be provided for the selected laboratory measurement.

Applicable laboratory results will be graded according to National Cancer Institute's Common Terminology Criteria for Adverse Events (NCI-CTCAE version 4.03). The worst NCI-CTCAE will be summarized by treatment group.

For non-fasting glucose, the screening measurement will be used as the baseline measurement. A listing of subjects with 1 or more NCI-CTCAE toxicity grade ≥ 2 in hematology and clinical chemistry laboratory measurements will be provided.

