12-lead ECG		X							X								X	
Tuberculosis evaluation	X	X	X	X	X	X	X	X	X	X	X	X	X	X	X	X	X	X
Chest radiograph	X																	
Urine pregnancy test ^d	X	X	X	X	X	X	X	X	X	X	X	X	X	X	X	X	X	X
Height		X																
Weight		X																
Concomitant therapy	X	X	X	X	X	X	X	X	X	X	X	X	X	X	X	X	X	X
Adverse events	X	X	X	X	X	X	X	X	X	X	X	X	X	X	X	X	X	X
eC-SSRS ^e	X	X				X	X	X	X	X	X	X	X	X	X	X	X	X

TIME AND EVENTS SCHEDULE

Phase	Screening ^a	Active Treatment															Follow-up	
Week		0	1	2	3	4	8	12	16	20	24	28	32	36	40	44	48 ^b	56
Study Procedures																		
Efficacy Assessments																		
IGA	X	X	X	X	X	X	X	X	X	X	X	X	X	X	X	X	X	X
PASI	X	X	X	X	X	X	X	X	X	X	X	X	X	X	X	X	X	X
Body Surface Area (BSA)%	X	X																
Clinical Laboratory Assessment																		
QuantiFERON-TB test ^f	X																	
Hepatitis B and C serology	X																	
HIV antibody test	X																	
Hematology	X	X				X		X			X			X			X	X
Chemistry ^g	X	X				X		X			X			X			X	X
Lipid panel ^h		X																
Hs-CRP		X																
Pharmacokinetics and Immunogenicityⁱ																		
Serum guselkumab concentration		X				X		X		X		X				X		X
Antibodies to guselkumab		X				X		X		X		X				X		X
Biomarkers																		
Serum biomarkers ^j		X				X					X						X	
Skin biopsy (RNA) ^k		X				X					X							
██████████		█									█						█	

TIME AND EVENTS SCHEDULE

Phase	Screening ^a	Active Treatment														Follow-up		
Week		0	1	2	3	4	8	12	16	20	24	28	32	36	40	44	48 ^b	56
Study Procedures																		
Genetic (DNA) evaluations																		
Genetic (DNA) analyses ^m		X																

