- Alanine aminotransferase $\leq 2 \times$ ULN
- Alkaline phosphatase $\leq 2 \times$ ULN

Other inclusion criteria

16. Agree to avoid prolonged sun exposure and avoid use of tanning booths or other ultraviolet light sources during study.
17. Be willing and able to adhere to the prohibitions and restrictions specified in this protocol.
18. Must sign an informed consent form (ICF) [(or their legally acceptable representative must sign)] indicating that he or she understands the purpose of, and procedures required for, the study and is willing to participate in the study.
19. Must sign a separate ICF if he or she agrees to provide an optional DNA sample for research (where local regulations permit). Refusal to give consent for the optional DNA research sample does not exclude a subject from participation in the study.

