2.6.2. Baseline

In general, the baseline measurement is defined as the closest measurement taken prior to or at the time of the first study agent administration date unless otherwise specified.

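### SAP 6.2 tabulates the worst NCI-CTCAE laboratory grade by arm without relating it to baseline grade, so persisting entry abnormalities are counted with new or worsened ones

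*SAP*

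**What the plan says.** SAP 6.2 grades applicable laboratory results by NCI-CTCAE version 4.03 and then states that "The worst NCI-CTCAE will be summarized by treatment group". It adds box plots of values and change from baseline for selected tests, and a listing of subjects with grade 2 or higher. Neither the summary nor the listing is limited to post-baseline values or refers to baseline grade.

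Protocol 11.8 plans summaries of laboratory values and their change from baseline. It says grades will be used in summarising laboratory data, and it promises: "A listing of subjects with post-baseline abnormal laboratory results based on NCI-CTCAE grades will also be provided".

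A baseline is available. SAP 2.6.2 says that, in general, "the baseline measurement is defined as the closest measurement taken prior to or at the time of the first study agent administration date", and SAP 6.2 adds: "For non-fasting glucose, the screening measurement will be used as the baseline measurement". No graded output is stated to use either rule.

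Other safety domains do refer to baseline:
- Protocol 11.8 includes "AEs that have worsened since baseline" among the adverse events analysed.
- SAP 6.4 summarises post-baseline ECG abnormalities that differ from Week 0.
- SAP 6.5 gives a shift table from baseline for the eC-SSRS categories.

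**The concern.** SAP 6 says that laboratory safety is assessed by looking at changes in the parameters. A worst-grade count is not a measure of change. If a subject enters at grade 1 and stays there, the table shows a grade 1 subject, exactly as it would for someone who entered normal and became grade 1 on treatment. Limiting the table to post-baseline values, as Protocol 11.8 does for its listing, would not separate the two, because a persisting value is also a post-baseline value.

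At stake is the number of subjects per arm whose laboratory grade became worse on treatment. The loss falls mainly on low-grade changes that the investigator does not judge clinically relevant, since those do not reach the adverse event tables.

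**Working it through.** The plan gives no figure for laboratory grades, so there is none to reproduce. The check has three parts.

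**1. Does any planned output supply the missing count?**

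| Output | Where | Uses grade? | Related to baseline? | Count by arm? |
|---|---|---|---|---|
| Worst grade | SAP 6.2 | Yes | No | Yes |
| Grade 2 or higher listing | SAP 6.2 | Yes | No | No, subject listing |
| Post-baseline abnormal listing | Protocol 11.8 | Yes | Timing only | No, subject listing |
| Change from baseline; box plots | Protocol 11.8; SAP 6.2 | No, values | Yes | No |
| Adverse event tables | Protocol 11.8; SAP 6.1 | No, investigator judgement | Yes | Yes |

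No row combines all three properties.

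**2. Can entry abnormalities occur?** SAP 6.2 names 7 hematology and 14 chemistry analytes, 21 in all. Inclusion Criterion 15 sets limits for 8: hemoglobin, white cells, neutrophils, platelets, creatinine, AST, ALT and alkaline phosphatase. The other 21 − 8 = 13 have no numeric limit. AST, ALT and alkaline phosphatase may be up to 2 × ULN, so values above normal are allowed. Exclusion Criterion 1 bars severe, progressive or uncontrolled disease, so most entry abnormalities should be low grade. Which analytes are gradable, and at what cut-offs, is not in the documents.

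**3. How much could this matter?** The Time and Events Schedule has hematology and chemistry at Weeks 4, 12, 24, 36, 48 and 56, which is 6 post-baseline draws. Three inputs are assumed, because the documents give none of them:
- e: proportion of subjects at the grade at baseline
- q: chance that such a subject is at the grade at any one later draw
- t: rate of newly reaching the grade among the rest

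Let p be the chance that an entry case is counted. With independent draws p = 1 − (1 − q)^6. With perfectly correlated draws p = q. If baseline values are themselves included, as the SAP sentence permits, p = 1.

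Pre-existing share of subjects tabulated = e·p / (e·p + (1 − e)·t).

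| e | q | t | p, independent | Share, independent | Share, perfectly correlated | Share, baseline included |
|---|---|---|---|---|---|---|
| 1% | 10% | 10% | 46.9% | 4.5% | 1.0% | 9.2% |
| 1% | 25% | 5% | 82.2% | 14.2% | 4.8% | 16.8% |
| 5% | 25% | 5% | 82.2% | 46.4% | 20.8% | 51.3% |
| 10% | 25% | 5% | 82.2% | 64.6% | 35.7% | 69.0% |
| 10% | 50% | 2% | 98.4% | 84.5% | 73.5% | 84.7% |

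First row, independent draws: 0.01 × 0.469 / (0.01 × 0.469 + 0.99 × 0.10) = 0.00469 / 0.10369 = 4.5%. A persisting abnormality implies correlated draws, so the independent column leans high for a given q.

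Arm comparison: with the same e and p in both arms, the e·p term cancels and the tabulated difference is (1 − e)(t₂ − t₁). For an assumed 5% v 8%, a difference of 3.0 points becomes 2.97, 2.85 or 2.70 points at e = 1%, 5% or 10%.

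**The case against.** The strongest reply is that a worst-grade table by arm is a legitimate descriptive summary, and that a shift table is a choice of layout. Change from baseline in the values is already planned, all abnormal values are reviewed by the investigator (Protocol 9.6), and clinically relevant changes are recorded as adverse events. Screening and Week 0 values are collected, so the count could be derived at any time; only its pre-specified tabulation is absent. All of this stands, and it is why the point is small. It does not fill the gap, because none of these planned outputs gives the by-arm count.

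A second reply is that the documents do not show that any enrolled subject will carry a baseline grade. That is also right: a value between 1 and 2 × ULN is abnormal, but the grading cut-offs are not in the documents, and only applicable results are graded. The point is therefore about what the table would count if such subjects are enrolled.

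A reader might go further and infer that the table biases the comparison between arms or costs power to detect a laboratory signal. The documents do not support either reading. Entry grades are balanced in expectation by randomisation, the absolute difference barely moves in the illustration, and SAP 6 plans no formal safety testing, so power does not arise. A ratio of the two arms' percentages would be diluted towards 1, but the plan does not call for one.

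**Conclusion.** The point holds as a low-priority improvement. As written, SAP 6.2 neither limits the worst grade to post-baseline values nor relates it to baseline grade. Any persisting entry abnormality is counted with new and worsened grades, and no planned output separates them by arm.

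The size is unknown. The pre-existing share of subjects tabulated at a grade runs from roughly 5% to 85% across the assumed inputs with independent draws, and from about 1% to 74% at the same two extremes if draws within a subject are perfectly correlated. So wide a range is not an estimate for this trial. The conclusion that the arm comparison is not distorted rests on balanced entry grades and equal persistence in both arms. No efficacy conclusion is affected.

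**What to change.** In SAP 6.2, replace the worst-grade sentence with:

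> The worst post-baseline NCI-CTCAE grade will be cross-tabulated against baseline grade by treatment group for each graded analyte, and the number of subjects whose grade worsened from baseline will be summarized.

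Use the SAP 2.6.2 baseline, with the screening value for non-fasting glucose as SAP 6.2 already states. As an optional tidy-up, limit the grade 2 or higher listing to post-baseline results, in line with Protocol 11.8.

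The cost is a programming change to one table. Screening and Week 0 samples are already scheduled, so no new data, visits or tests are needed. The downside is a longer table.
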